## A Phase II Study of Stereotactic Body Radiotherapy (SBRT) for Prostate Cancer Using Continuous Real-time Evaluation of Prostate Motion and IMRT Plan Reoptimization based on Same Day Anatomy

**Principal Investigators** 

Radiation Oncology W. [name], MS, M. Ed. Department of Radiation Oncology Duke University [name] [contact] [contact] [contact]

Physics Q. [name]. Department of Radiation Oncology Duke University [name] [contact] [contact] [contact]

Version Date: June 17, 2013

NCT00941915

S	CHEMA	
Gleason Score		Treatment Arm
1. ≤6		
2. 7	dy	
PSA	Stu	7.4 Gy for 5 fractions
1. $\leq$ 15 ng/mL if Gleason $\leq$ 6	ц	delivered every other day;
2. $\leq 10 \text{ ng/mL}$ if Gleason 7	L O	IMRT/IGRT with
	ite	reoptimization for each
	.50	fraction
T stage	Se	
T1-2		

Treatment is prescribed as a minimum to the planning target volume (PTV) to be delivered at a daily dose of 7.4 Gy/ fraction. The PTV includes with CTV (prostate only) with a nonuniform margin.

Patient Population: (See Section 3.0 for Eligibility)

- Histologically confirmed prostate adenocarcinoma within 365 days prior to registration
- Clinical stage T1-2 according to the AJCC 6th edition
- Pretreatment PSA ≤10 ng/mL if Gleason 7 or ≤ 15 ng/ml if Gleason ≤6 (within 180 days of registration)
- Gleason score must be  $\leq 7$
- No previous radical surgery or cryosurgery for prostate cancer
- No prior or planned androgen deprivation or bilateral orchiectomy

## 1.0 Introduction

# 1.1 Conventionally Fractionated External Beam Radiotherapy

The optimal radiation schedule taking into account both daily fraction size and overall duration of treatment for the curative treatment of prostate cancer using external beam radiation therapy (EBRT) is unknown. Over the last 10 years it has been typical for most patients to receive daily fractions of 1.8-2.0 Gy for a duration of 7-8 weeks to a total cumulative dose to the prostate of 70-79 Gy (1). Treatment in this fashion has been demonstrated to be safe with moderate rates of late rectal and bladder toxicity.

Four randomized trials provide evidence that doses above 74 Gy can increase the likelihood of cure but higher doses are associated with increased toxicity, especially rectal toxicity (2-5). In the MD Anderson randomized trial there was an increase in grade 2 or higher rectal toxicity from 12% to 26% between the 70 Gy and 78 Gy arms (6). In further analysis of this study it was found that both the volume of rectum treated to higher doses (70 Gy) as well as lower doses (40-60 Gy) contributed to late rectal toxicity (7). Further dose intensification using conventional fractions of 1.8-2.0 Gy is not likely to provide significant further gains without coincident increases in late toxicity because the anterior rectal wall and prostate are in close physical proximity. Even with the most successful radiation targeting one will not be able to adequately treat the prostate without also treating a portion of the anterior rectal wall. Additionally, the delivery of radiation therapy over this protracted period of time is expensive and inconvenient for patients with some radiation schedules in excess of 9 weeks.

We propose to investigate a novel treatment regimen that will: 1) significantly reduce the duration of treatment and 2) limit the volume of normal tissue radiated while maintaining equivalent efficacy. In short, we hypothesize that hypofractionated radiation therapy using continuous real-time evaluation of prostate motion combined with reoptimization of the IMRT plan according to the anatomy of the day will improve the therapeutic ratio.

# **1.2 Biologic Basis of Hypofractionation**

The efficacy of radiation in causing reproductive cellular death is a function of the overall radiation dose, the dose per fraction, and the overall treatment time. Classically this relationship is described according to the linear-quadratic (LQ) model. Using the LQ model the fractionation sensitivity of both tumor cells and normal tissues can be defined using the alpha-beta ratio ( $\alpha/\beta$ ).

Rapidly dividing tumors or acute responding normal tissues are generally described by a high alpha-beta ratio ( $\geq 10$  Gy) such that changes in individual fraction size would be expected to only have a modest overall impact on efficacy as compared to overall treatment dose. In contrast, slowly dividing tissues that exhibit late toxicity to radiation therapy (such as bone, connective tissues, or spinal cord) are often described by a lower alpha-beta ratio (in the range of 3-5 Gy) such that larger daily fractions would be anticipated to cause relatively greater toxicity when compared to smaller fractions when delivered to the same total dose. In most clinical scenarios cancers have alpha-beta ratios much higher than the normal tissues adjacent to them (*i.e.* 10 Gy vs. 3 Gy) and as a result

conventional radiation fractions of 1.8-2.0 Gy have the greatest likelihood of maintaining an advantageous therapeutic ratio as radiation doses are escalated.

There is accumulating evidence that prostate cancer may have a lower alpha-beta ratio than nearby normal tissues (rectum, bladder) (8). This observation has encouraged investigators to evaluate radiation fractionation schemes that use fraction sizes larger than 1.8-2.0 Gy (9). If the alpha-beta ratio of prostate cancer is lower than nearby normal tissues then treating prostate cancer with fewer, larger fractions (to a lower total dose) should result in an increase in the therapeutic ratio.

# **1.3** Hypofractionation in Prostate Cancer

In the last decade investigators from across the globe have examined a number of hypofractionated regimens with daily fraction sizes ranging from 2.5 to 7.25 Gy delivered in 5-28 fractions over 1-6 weeks (10). As this protocol examines a five fraction regimen, only the experience with five fraction regimens will be reviewed.

Investigators at the Virginia Mason Clinic in Seattle published the first experience with a five fraction regimen in 2006 (11). These clinicians treated a total of 40 patients with low risk prostate cancer (T2a or less, Gleason 6 or less, PSA 10.0 or less) and reported preliminary toxicity and efficacy results with a median follow-up of 41 months. The Virginia Mason clinicians delivered five fractions of 6.7 Gy (total dose 33.5 Gy) over five days.

The 5 year estimate of freedom from biochemical recurrence is 90% by RTOG-Phoenix definition. Late toxicity was defined as occurring 30 or more days after the completion of therapy. Overall, the treatment was well tolerated with no Grade 3-5 genitourinary (GU) or gastrointestinal (GI) toxicity reported at a median of 41 months of follow-up. Grade 2 genitourinary toxicity was reported in 20% (8/40) of patients and Grade 2 gastrointestinal toxicity was reported in 7.5% (3/40) of patients.

The second published experience with a five fraction regimen comes from investigators at Stanford University (12). These clinicians treated a total of 41 patients with low risk prostate cancer (T2a or less, Gleason 6 or less, PSA 10.0 or less) and reported preliminary toxicity and efficacy results with a minimum follow-up of 6 months (median 33 months). The Stanford regimen delivered 5 fractions of 7.25 Gy over 1-2 weeks.

The Stanford investigators reported no RTOG Grade 4-5 acute or late GU/GI complications. Two patients experienced RTOG Grade 3 late GU toxicity and none reported Grade 3 GI complications. A reduced rate of rectal toxicities was observed with every-other-day vs. 5 consecutive days treatment regimen (0% vs. 38%, p = 0.0035). At last follow-up, no patient has had a biochemical recurrence. Of 32 patients with 12 months minimum follow-up, 25 patients (78%) achieved a PSA nadir  $\leq$ 0.4 ng/mL. A PSA decline to progressively lower nadirs up to 3 years after treatment was observed.

# 2.0 Objectives

# 2.1 Primary Objective

To evaluate the incidence of GU and GI acute and late toxicity (see Section 8.1) for patients treated with prostate stereotactic body radiotherapy (SBRT) along with prostate

localization (Calypso or ExacTrac and onboard cone-beam CT) and IMRT reoptimization for each fraction based on the anatomy of the day.

# 2.2 Secondary Objectives

- 2.2.1 Disease-free survival: Disease-free failure events include local progression, distant progression, biochemical failure as defined by the RTOG Phoenix definition, and death from any cause.
- 2.2.2 Evaluate patient quality of life (QOL) using the Expanded Prostate Cancer Index Composite 26 (EPIC-26) for evaluation of the QOL for up to 3 years after the completion of SBRT.

# 2.3 Duration of Investigation and Expected Enrollment Rate

Men will be enrolled on study after meeting eligibility criteria and signing consent. Followup will continue for each enrollee up to three years after enrollment. It is estimated that a subject will be involved in the study for 36 months. We anticipate that this study will begin enrolling subjects in the Fall 2009 and will enroll 2 subjects a month for 30 months for a total enrollment of 60.

# 3.0 Study Design and Patient Selection

# 3.1 Study Design

This is a Phase II single institution investigator-initiated trial where the primary end-point is the assessment of Grade 2+ late toxicity 2 years from the start of treatment. Based upon an assumed linear rate of grade 2 or greater toxicity from 18-36 months after the completion of treatment the primary end-point will be assessed when all patients have completed treatment, have a minimum of 3 months of follow-up, and a cumulative 120 person/years of follow-up have been recorded (an average of 2 years per patient).

# 3.2 Inclusion Criteria

- 3.2.1 Histologically confirmed diagnosis of adenocarcinoma of the prostate within 365 days of study enrollment
- 3.2.2 History/physical examination with digital rectal examination of the prostate within 8 weeks prior to study enrollment
- 3.2.3 Gleason score  $\leq 7$
- 3.2.4 Clinical Stage T1-T2c
- 3.2.5 PSA

 $\leq$  15 ng/ml prior to start of the rapy if Gleason  $\leq\!\!6$  OR

 $\leq$  10 ng/ml prior to start of therapy if Gleason 7

- 3.2.6 ECOG/Zubrod Performance Status 0-1
- 3.2.7 Age > 40
- 3.2.8 Patient signs study specific informed consent prior to study enrollment.

# **3.3** Exclusion Criteria

3.3.1 Prior or concurrent invasive malignancy (except non-melanomatous skin cancer) or lymphomatous/hematogenous malignancy unless continually disease free for a

minimum of 5 years. (For example, carcinoma in situ of the bladder or oral cavity is permissible)

- 3.3.2 Evidence of distant metastases (based on disease stage and clinical presentation)
- 3.3.3 Evidence of regional lymph node involvement (based on disease stage and clinical presentation)
- 3.3.4 Significant urinary obstruction (i.e. AUA Symptom score > 18)
- 3.3.5 Estimated prostate gland > 100 grams (within 8 weeks prior to study enrollment)
- 3.3.6 Previous radical surgery (prostatectomy) or cryosurgery for prostate cancer
- 3.3.7 Previous pelvic irradiation, prostate brachytherapy, or bilateral orchiectomy
- 3.3.8 Previous hormonal therapy, such as LHRH agonists (e.g. goserelin, leuprolide), anti-androgens (e.g., flutamide, bicalutamide), estrogens (e.g., DES), or surgical castration (bilateral orchiectomy) or planned concurrent androgen deprivation therapy
- 3.3.9 Previous or concurrent cytotoxic chemotherapy for prostate cancer
- 3.3.10 Prosthetic implants in the pelvic region that contain metal or conductive materials (e.g., an artificial hip).
- 3.3.11 Severe, active comorbidity, defined as follows:
  - Unstable angina and/or congestive heart failure requiring hospitalization within the last 6 months
  - Transmural myocardial infarction within the last 6 months
  - Acute bacterial or fungal infection requiring intravenous antibiotics at the time of registration
  - Crohn's Disease or ulcerative colitis
  - Chronic obstructive pulmonary disease exacerbation or other respiratory illness requiring hospitalization or precluding study therapy at the time of registration
  - Hepatic insufficiency resulting in clinical jaundice and/or coagulation defects; note, however, that laboratory tests for liver function and coagulation parameters are not required for entry into this protocol. (Patients on Coumadin or other blood thinning agents are eligible for this study.)
  - Acquired immune deficiency syndrome (AIDS) based upon current CDC definition; note, however, that HIV testing is not required for entry into this protocol. The need to exclude patients with AIDS from this protocol is necessary because the treatments involved in this protocol may be significantly immunosuppressive. Protocol-specific requirements may also exclude immunocompromised patients.

## 4.0 Pretreatment Evaluations

Note: This section lists baseline evaluations needed before the initiation of protocol treatment that do not affect eligibility.

## 4.1 Symptom Assessment and QOL Evaluation

(These may be performed prior to consent as they are routine for urology or radiation oncology clinics);

4.1.1 International Prostate Symptom Score (IPSS)/American Urological Association Symptom Score, International Index of Erectile Function (IIEF-5) and EPIC-26 QOL.

## 4.2 Insurance Pre-Authorization

As some private insurance carriers will not cover SBRT to the prostate it is highly recommended that pre-authorization be completed before enrolling the patient on study. Patients whose insurance carriers do not cover SBRT of the prostate need to be advised before proceeding with study enrollment.

# 5.0 Radiation Therapy

#### 5.1 Dose Specifications

5.1.1 Stereotactic Targeting and Treatment This protocol will require treatments to be performed with a stereotactic technique with the use of a 3-D coordinate system defined by implanted transponders (Calypso) or use of the ExacTrac system and/or use cone-beam CT (CBCT) with fiducial markers.

**Dose Fractionation** 

Patients will receive 5 fractions of radiation. Each fraction size will be 7.4 Gy. The total dose will be 37 Gy. The 5 treatments will be scheduled to be delivered every other day. A minimum of 36 hours should separate each treatment. No more than 3 fractions will be delivered per week. The total duration of treatment will be no shorter than 10 days and no longer than 18 days.

## 5.2 Supportive Measures

5.2.1 Urinary

Symptomatic urinary medicines, (e.g. tamsulosin) are allowed at the discretion of the treating radiation oncologist or urologist.

5.2.2 Bladder

Patients will be asked to have a full urinary bladder both during simulation and treatment. This may be achieved by asking patients to drink 16-24 oz of water or other fluid 2-3 hours prior to treatment and to not urinate between this time and treatment as they are able.

## 5.2.3 Bowel

One tablespoon of Milk of Magnesia will be taken the night before the simulation and the night before each treatment. One Fleet's enema will be administered 2-3 hours before the simulation and each treatment.

## 5.3 Technical Factors

5.3.1 Radiotherapy delivery

Megavoltage radiation therapy will be utilized with 6 to 21 MV photons. Standard quality assurance measures will be taken prior and during radiation therapy.

## 5.4 Set-up, Localization and Tracking

5.4.1 Patient Set-up

Patients will be positioned supine in a comfortable posture. The minimum immobilization apparatus will be a pillow under the knees and the feet taped or rubber-banded together or equivalent. More complex immobilization devices are allowed, as per the discretion of the treating physician, as long as they do not

interfere with the proper functioning of the image-guidance (Calypso, ExacTrac and cone-beam CT) system.

5.4.2 Localization

The Calypso or ExacTrac or cone-beam CT system will be utilized for both localization and tracking/monitoring. The initial localization and alignment is based on the center of mass of the transponders/fiducial markers. After initial localization is performed, all effort should be made to initiate the treatment delivery as quickly as possible. Significant rotations may be corrected at initial localization stage, and intra-fractional rotations will be ignored. Further adjustment during the treatment will be translational shift of the center of mass determined via Calypso or ExacTrac, using remote couch motion.

# 5.5 Treatment Planning

5.5.1 Simulation

Computed Tomography (CT)

CT will be the primary image platform for treatment planning. The simulation should be performed in the supine treatment position, with the transponders/fiducial markers in place. Axial cuts of 3 mm or less will be acquired throughout the pelvis with slices of 1 mm thickness through the prostate (defined as 1 cm cranial to the cranial most point of the prostate gland or transponder/fiducial markers to 1 cm caudal to the prostate gland or inferior most transponder/fiducial marker).

# MRI

MRI images are not required. However, if MR scan is planned with use of Calypso system, MR should be obtained prior to the implantation of transponders.

Contrast Oral, IV, urethral, and bladder contrast are allowed but not required.

5.5.2 Treatment Planning/Target Volumes

1. The definition of volumes will be in accordance with the ICRU Report #50 and ICRU Report #62: Prescribing, Recording, and Reporting Photon Beam Therapy. 2. The Gross Tumor Volume (**GTV**) is defined by the physician as all known disease as defined by the planning CT and MR along with clinical information. The GTV for the purposes of this protocol is the prostate only.

3. The clinical target volume (**CTV**) will be the same as the GTV and will consist of the prostate without the seminal vesicles as defined by non-contrast axial CT scan.

4. The planning target volume (**PTV**) will be defined as the CTV plus a 3 mm margin posteriorly and 5mm in all other dimensions.

## 5.5.3 Dosimetry

1. Intensity Modulated Radiotherapy (IMRT) beam arrangements will be designed with a minimum of 5 non-opposed fields. Rotational IMRT is also allowed provided it demonstrates equivalent dosimetry compared to standard IMRT. If

rotational IMRT delivery is used for planning, a corresponding fixed gantry IMRT plan should also be generated.

2. Axial or non-axial beam arrangements may be utilized as per institutional preference.

3. The prescription isodose line must encompass at least 95% of the PTV with a maximal differential between the prescription isodose line and the maximum dose to the PTV of 15%. Maximal dose to the PTV is defined as to 1cc or 1% of PTV. In addition, <10% of the PTV or < 5 cc (whichever is smaller) should be treated to >112% of the prescription dose.

4. Adequate dose conformality to the PTV, defined as the ratio of prescription isodose volume to PTV volume of < 1.2, should be achieved.

5. The volume of all tissues outside the PTV receiving > 100% of the prescription dose should be < 15% of PTV volume.

6. Ideally hot spots will be manipulated to occur within the peripheral zones of the prostate itself avoiding the prostate-rectal interface as defined by the CTV.

# 5.6 Critical Structures

5.6.1 Critical Organ Dose-Volume Limits

1. The normal tissue volume to be contoured will include bladder, rectum, bilateral femora (to the level of ischial tuberosity), seminal vesicles, penile bulb, and skin.

2. The normal tissues will be contoured and considered as solid organs.

3. The bladder should be contoured from its base to the dome

4. The rectum should be contoured from the anus (at the level of the ischial tuberosities) for a length of 15 cm or to the rectosigmoid flexure. This generally is below the bottom of the sacroiliac joints.

5. The seminal vesicles will be contoured from the cranial most aspect of the prostate superiorly as one structure (right and left). The seminal vesicles are not a target for this trial but dosimetric data will be collected for later analysis.

7. The tissue within the skin and outside all other critical normal

structures and PTVs are designated as unspecified tissue.

8. The following table lists maximum dose limits to a point or volume within several critical organs. These are absolute limits, and treatment delivery that does not abide by these limits will constitute a major protocol violation. The dose is listed as total over 5 fractions and per fraction.

Organ	Volume	Dose (Gy)
Prostate (PTV)	Maximum point dose (1cc)	$\leq$ 43.0 Gy (8.5 Gy per fraction)
		115% of prescription dose
	The smaller of 10% or 5 cc	$\leq$ 41.9 Gy (8.3 Gy per fraction)
		112% of prescription dose
	Minimum 95%	$\geq$ 37 Gy (7.4 Gy per fraction)
		100% of prescription dose
Rectum	Maximum point dose (1cc)	$\leq$ 39.3 Gy (7.8 Gy per fraction)
		105% of the prescription dose

	Less than 2 cc	> 37  Gy (7.4  Gy per fraction)
		100% of prescription dose
	75% rectum	$\leq$ 33 Gy (6.6 Gy per fraction)
		90% of prescription dose
	60% rectum	≤28 Gy (5.6 Gy per fraction)
		75% of prescription dose
	50% rectum	$\leq$ 24 Gy (4.8 Gy per fraction)
		65% of prescription dose
Bladder	Maximum point dose (1cc)	40.7 Gy (8.14 Gy per fraction)
		110% of prescription dose
	Less than 40 cc	>24 Gy (4.8 Gy per fraction)
		65% of prescription dose
Penile bulb	Maximum point dose	No more than 100% of prescription
		dose
	Less than 3 cc	20 Gy (4 Gy per fraction)
		54% of prescription dose
Femoral heads	Less than 10 cc cumulative	20 Gy (4 Gy per fraction)
Skin	(both sides)	54% of prescription dose
	Maximum point dose	30 Gy (6 Gy per fraction)
		81% of prescription dose
Seminal Vesicles	No dose constraint	Collect for documentation only

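### Three total-dose limits in the Section 5.6.1 table (43.0, 41.9 and 39.3 Gy) are about 0.45 Gy above the percentages of 37 Gy printed beside them

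*Combined protocol and SAP*

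**What the plan says.** Section 5.1 (Dose Fractionation) prescribes 5 fractions of 7.4 Gy, 37 Gy in all. The table in Section 5.6.1 uses the same base: its 100% rows read 37 Gy and 7.4 Gy per fraction.

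Item 8 of Section 5.6.1 introduces the table with "These are absolute limits, and treatment delivery that does not abide by these limits will constitute a major protocol violation" and adds: "The dose is listed as total over 5 fractions and per fraction". Most rows also give a percentage of the prescription. The three rows at issue are:

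- PTV, maximum to 1 cc: "43.0 Gy (8.5 Gy per fraction"), labelled 115%.
- PTV, smaller of 10% or 5 cc: "41.9 Gy (8.3 Gy per fraction"), labelled 112%.
- Rectum, maximum to 1 cc: "39.3 Gy (7.8 Gy per fraction"), labelled 105%.

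Section 5.5.3, item 3, states the two PTV criteria separately. It allows a "maximal differential between the prescription isodose line and the maximum dose to the PTV of 15" percent, with the maximum taken to 1 cc or 1% of the PTV, and it repeats the 112% hot-spot criterion. It gives no second statement of the rectal 1 cc limit. Neither section gives a rounding rule or an order of precedence among total, per-fraction dose and percentage.

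**The concern.** Three expressions of one limit should agree to the precision printed. In these rows the total is higher than both the percentage and the per-fraction dose allow, always in the permissive direction. Because a breach counts as a major violation, two people could classify the same treatment differently.

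- **PTV 1 cc at 42.8 Gy.** This is within the printed 43.0 Gy, but it is 42.8/37 = 115.7% of prescription and 42.8/5 = 8.56 Gy per fraction.
- **Rectum 1 cc at 39.1 Gy.** This is within the printed 39.3 Gy, and 39.1/5 = 7.82 rounds to the printed 7.8 Gy per fraction, but it is 39.1/37 = 105.7% against a limit of 105%.

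The rectal row deserves the most care. Section 7.1 bases its power statement on grade 3 or higher rectal toxicity, and no other section restates this limit. What is at stake is plan acceptance and violation classification only.

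**Working it through.** **Inputs.** Prescription 5 × 7.4 = 37 Gy (Section 5.1). Totals, per-fraction doses and percentages come from the Section 5.6.1 table.

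**Step 1: total against percentage × 37 Gy.**

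| Row | Printed total | Percent × 37 | Gap | Total as % of 37 |
|---|---|---|---|---|
| PTV 1 cc, 115% | 43.0 | 42.55 | +0.45 | 116.22% |
| PTV 10%/5 cc, 112% | 41.9 | 41.44 | +0.46 | 113.24% |
| Rectum 1 cc, 105% | 39.3 | 38.85 | +0.45 | 106.22% |

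The totals are printed to 0.1 Gy, so rounding could explain a gap of at most 0.05 Gy.

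**Step 2: total against per-fraction dose.**

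| Row | Total/5 | Printed per fraction | Largest total that rounds to it | Percent × 7.4 |
|---|---|---|---|---|
| PTV 1 cc | 8.60 | 8.5 | 8.55 × 5 = 42.75 | 8.510 |
| PTV 10%/5 cc | 8.38 | 8.3 | 8.35 × 5 = 41.75 | 8.288 |
| Rectum 1 cc | 7.86 | 7.8 | 7.85 × 5 = 39.25 | 7.770 |

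Each printed total exceeds the largest value consistent with its own per-fraction dose. The per-fraction doses agree with the percentages to the 0.1 Gy shown, so the total is the odd figure in each row.

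**Step 3: the other 10 rows.** Total/5 equals the printed per-fraction dose exactly in all ten (7.4, 7.4, 6.6, 5.6, 4.8, 8.14, 4.8, 4, 4, 6). Total minus percent × 37 is 0, 0, −0.30, +0.25, −0.05, 0, −0.05, +0.02, +0.02 and +0.03 Gy. The two larger gaps come from whole-Gy rounding in the 75% rectum row, "33 Gy (6.6 Gy per fraction") against 33.3 Gy, and the 60% rectum row, "28 Gy (5.6 Gy per fraction") against 27.75 Gy. The bladder 1 cc row is exact on all three expressions (110% × 37 = 40.7 Gy; 40.7/5 = 8.14).

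**Step 4: how far the per-fraction figure settles intent.** If a per-fraction limit is read as rounded to 0.1 Gy, the share of each disputed band that still satisfies it is:

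- PTV 1 cc: (42.75 − 42.55)/0.45 = 44%
- PTV 10%/5 cc: (41.75 − 41.44)/0.46 = 67%
- Rectum 1 cc: (39.25 − 38.85)/0.45 = 89%

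On that reading the per-fraction dose says little about the rectal row. Read literally, 7.8 × 5 = 39.0 Gy, which is nearer 38.85 than 39.3.

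**Step 5: a possible origin.** 37.4 × 1.15 = 43.01, 37.4 × 1.12 = 41.89 and 37.4 × 1.05 = 39.27, which round to the three printed totals. A base of 37.4 instead of 37 Gy would explain all three. The documents do not say so; this is inference, and the finding does not depend on it.

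**The case against.** The arithmetic is hard to dispute; the objections concern consequence and reading.

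- **No analysis uses violation status.** Section 7 excludes no one for a dosimetry violation, and analyzable patients are defined in Section 7.4 by eligibility and receipt of some treatment. This stands, and it is why the point is minor.
- **Section 5.5.3 already governs the PTV.** A planner following its 15% and 112% criteria would not accept a plan in either PTV band. This also stands, but that section attaches no violation class and does not cover the rectal limit.
- **All three expressions are upper bounds, so meeting the strictest meets them all.** True, and nobody is forced to break one limit to satisfy another. But no strictest-figure rule is written, and under one the three printed totals would never operate.
- **Item 8 names total and per-fraction dose, not percent, so Gy may be the operative form.** This does not settle the matter, because those two Gy figures also disagree in these rows.
- **The corrected totals are not exactly five times the printed per-fraction doses.** They give 8.51, 8.288 and 7.77 against 8.5, 8.3 and 7.8. They agree to the 0.1 Gy shown, and a precedence sentence settles the remaining 0.01 to 0.03 Gy.
- **The violation is defined on delivery, not on the plan.** This is fair: with reoptimization possible at each fraction, an initial plan value in a band does not by itself establish a violation.

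**Conclusion.** The concern holds and is minor. Three of 13 rows carry a total that conflicts with both other figures in the row, by 0.45 to 0.46 Gy, always permissively. The disputed bands are 42.55–43.0 Gy (PTV 1 cc), 41.44–41.9 Gy (PTV 10%/5 cc) and 38.85–39.3 Gy (rectum 1 cc).

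This rests on the prescription being 37 Gy and on the percentages referring to it, both of which the protocol states. For the PTV rows the intended limit is clear, because Section 5.5.3 confirms the percentages. For the rectum, 105% points to 38.85 Gy but nothing else in the documents confirms it. Nothing shows that any patient's dose fell in a disputed band.

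**What to change.** 1. Change the PTV 1 cc total to 42.55 Gy and the PTV 10%/5 cc total to 41.44 Gy, in line with Section 5.5.3.
2. Have the investigator and physicist confirm the intended rectum 1 cc limit: 38.85 Gy if 105% is meant.
3. Add one sentence to item 8 saying which expression decides a major violation. This also covers the 60% and 75% rectum rows, where whole-Gy rounding leaves small differences.
4. As a precaution, check the planning records for values in the three bands, and review any hit against the dose actually delivered. The Appendix 3 worksheet cannot settle the rectal row, because it records dose to 2 cc of rectum, not 1 cc; the treatment planning system is the source.

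The cost is very low: two corrected values, one confirmation, one sentence and one look-up. No analysis has to change.
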